5.3.3.2 Assent of subjects who are not yet adults

Indicate whether assent will be obtained from all, some, or none of the children. If assent will be obtained from some children, indicate which children will be required to assent. When assent of children is obtained describe whether and how it will be documented.

Not applicable.

6.0 HIPAA Research Authorization and/or Waiver or Alteration of Authorization

This section is about the access, use or disclosure of Protected Health Information (PHI). PHI is individually identifiable health information (i.e., health information containing one or more 18 identifiers) that is transmitted or maintained in any form or medium by a Covered Entity or its Business Associate. A Covered Entity is a health plan, a health care clearinghouse or health care provider who transmits health information in electronic form. See the "Investigator Manual (HRP-103)" for a list of the 18 identifiers. HRP-103 can be accessed by clicking the Library link in CATS IRB (<http://irb.psu.edu>).

If requesting a waiver/alteration of HIPAA authorization, complete sections 6.2 and 6.3 in addition to section 6.1. The Privacy Rule permits waivers (or alterations) of authorization if the research meets certain conditions. Include only information that will be accessed with the waiver/alteration.

6.1 Authorization and/or Waiver or Alteration of Authorization for the Uses and Disclosures of PHI

Check all that apply:

- Not applicable, no identifiable protected health information (PHI) is accessed, used or disclosed in this study.** *[Mark all parts of sections 6.2 and 6.3 as not applicable]*
- Authorization will be obtained and documented as part of the consent process.** *[If this is the only box checked, mark sections 6.2 and 6.3 as not applicable]*
- Partial waiver is requested for recruitment purposes only (Check this box if patients' medical records will be accessed to determine eligibility before consent/authorization has been obtained).** *[Complete all parts of sections 6.2 and 6.3]*
- Full waiver is requested for entire research study (e.g., medical record review studies).** *[Complete all parts of sections 6.2 and 6.3]*
- Alteration is requested to waive requirement for written documentation of authorization (verbal authorization will be obtained).** *[Complete all parts of sections 6.2 and 6.3]*

6.2 Waiver or Alteration of Authorization for the Uses and Disclosures of PHI

6.2.1 Access, use or disclosure of PHI representing no more than a minimal risk to the privacy of the individual

6.2.1.1 Plan to protect PHI from improper use or disclosure

Include the following statement as written – DO NOT ALTER OR DELETE unless this section is not applicable because the research does not involve a waiver of authorization. If the section is not applicable, remove the statement and indicate as not applicable.

Not applicable.

6.2.1.2 Plan to destroy identifiers or a justification for retaining identifiers

Describe the plan to destroy the identifiers at the earliest opportunity consistent with the conduct of the research. Include when and how identifiers will be destroyed. If identifiers will be retained, provide the legal, health or research justification for retaining the identifiers.

Not applicable.

6.2.2 Explanation for why the research could not practically be conducted without access to and use of PHI

Provide an explanation for why the research could not practically be conducted without access to and use of PHI.

Not applicable.

6.2.3 Explanation for why the research could not practically be conducted without the waiver or alteration of authorization

Provide an explanation for why the research could not practically be conducted without the waiver or alteration of authorization.

Not applicable.

6.3 Waiver or alteration of authorization statements of agreement

By submitting this study for review with a waiver of authorization, you agree to the following statement – DO NOT ALTER OR DELETE unless this section is not applicable because the research does not involve a waiver or alteration of authorization. If the section is not applicable, remove the statement and indicate as not applicable.

Not applicable.

7.0 Study Design and Procedures

7.1 Study Design

Describe the type/design of trial to be conducted (e.g., double-blind, placebo controlled, parallel design, etc.). Provide a schematic diagram of study design, procedures and stages, if appropriate.

We propose a single-group pre-post behavioral intervention trial (N=30) with an ancillary lab study on a sub-sample (n=10) to gather mechanistic data on changes in microvascular function.

7.2 Study Procedures

Provide a description of all research procedures being performed and when they are being performed (broken out by visit, if applicable), including procedures being performed to monitor subjects for safety or minimize risks. Include any long-term follow-up procedures and data collection, if applicable.

Describe where or how you will be obtaining information about subjects (e.g., medical records, school records, surveys, interview questions, focus group topics, audio or video recordings, data collection forms, and collection of specimens through invasive or non-invasive procedures to include the amount to be collected and how often). Add any data collection instruments that will be seen by subjects to your study in CATS IRB (<http://irb.psu.edu>) in the “Supporting Documents” page.

7.2.1 Screening

Provide a description as defined above and format accordingly.

Screening for this study is a multi-step process. Interested participants may contact the researchers to determine their eligibility for the study. During the initial screening process, participants will be asked a number of questions to determine their eligibility (re: inclusion/exclusion criteria) as well as respond to the items of the PAR-Q which will be assessed over the phone. From there, interested and provisionally-eligible participants will be mailed an Actigraph accelerometer with a 1-week wear log (to verify <90 min/week of moderate or greater intensity PA) and a research assistant will call these participants to provide training on how to wear the device. After wearing the accelerometer for 1 week, provisionally-eligible participants will return the accelerometer via mail. Eligible participants (those that completed <90 min/week of moderate or greater intensity PA) will be contacted and scheduled for a lab visit. Those that are not eligible will be contacted and told they are not eligible to participate and thanked for their time. Eligible participants will be instructed prior to arriving for testing to drink water but to fast for 12 hours, no caffeine, and not to engage in exercise for 24 hours before.

7.2.2 Lab Visit 1 (Month 0)

During the lab visit 1, participants will provide informed consent to participate in the study by permitting their data to be used for research purposes. As the first step, participants will be asked to complete a baseline assessment which includes demographic questions, anthropometrics (height, weight), questions assessing motivation and enjoyment of PA and usual engagement in physical activity (international physical activity questionnaire). Participants will also complete a timed sorting task on a lab computer. Following this, approved research staff will install an application, HeartPhone, onto the participants' smartphone and instruct them on how to use the app. The research assistant will provide the participant with a Fitbit activity monitor and will load the Fitbit app on the participant's phone. Participants will provide permission to share their Fitbit data with the research team. Participants will not be told to increase their physical activity while enrolled in the study. Rather, a primary aim of the intervention is to examine whether the app is associated with any changes in their physical activity.

The HeartPhone application alters the background of a splash screen that appears when participants activate their screens. The background has images of physical activity and pleasant stimuli (example screen shots included as appendix). The app records the duration between turning the smartphone on and advancing to the next screen, date and time, and the number of attempts before the correct password is entered. These data are transmitted to a server maintained by the research team.

[name] has been working with [name] in HHD regarding the app. We do not believe that there will be an issue with our app as it utilizes a vendor hosted solution for data (no Penn State security issues) and there is no personally identifiable information stored on the server (our participant privacy/security will not be compromised). We have contacted [name] and in the event that he believes that we need to submit to OIS, we will do so

Participants will then be escorted over to Noll lab for assessments of:

- a. heart rate (HR)
- b. blood pressure (BP)
- c. oral temperature
- d. blood draw
- e. macrovascular function
- f. microvascular function (only for those in the ancillary study)Participants will also complete two fitness tests including the YMCA step test and a cycle ergometer test to assess aerobic function.

The nurse draws about 30 ml (2 Tbsp) of blood from a vein in the subject's arm. We send the blood to labs for some analyses. If the subject takes thyroid hormone, we draw an extra 3.5 ml (0.2 Tbsp) to check the level of thyroid hormone. Screening tests performed on blood: CBC, Lipid panel, and blood chemistry, Interleukin Panel (IL), folic acid and B12, homocysteine, oxidized LDL, total antioxidant capacity. We do not perform genetic analyses on the blood nor look for presence of disease (e.g. HIV).

Macrovascular Function: Flow Mediated Dilation (FMD)

FMD is an assessment of conduit vessel endothelial function. A blood pressure cuff is placed on the forearm, gel on the upper arm just above the elbow, and a Doppler ultrasound probe on the gel. The ultrasound measures vessel size and blood velocity. After a 3-minute "resting" measurement, we inflate the cuff for 5 minutes to occlude forearm blood flow. After deflating the cuff, we perform a second reading.

Microvascular Function: Microdialysis (MD)

The MD experiment directly quantifies nitric oxide-mediated vasodilation in the microcirculation. Subjects undergo MD at baseline. They repeat MD 3 and 6 months after the baseline experiment.

Preparation for all MD experiments:

Women of childbearing potential undergo a urine pregnancy test.

The participant washes a ventral forearm with antimicrobial soap.

The participant washes a ventral forearm with antimicrobial soap.

Microdialysis probe insertion:

A tight band is placed around the participant's arm to visualize veins.

For each MD site, a pair of pen-marks is made on the arm 2.5 cm (1 inch) apart and away from veins. The tight band is removed. The MD tubing enters and exits the skin at the marks.

The participant's ventral forearm is cleaned with povidone iodine and alcohol, and an ice bag is placed on the arm for 5 minutes to numb the skin. Then a thin needle is inserted into the skin at each entry mark. The needle's tip travels between the layers of skin for 2.5 cm (1 inch) and exits the skin at the matching exit mark. The MD tubing is threaded through the needle, and then the needle is withdrawn leaving the tubing in the skin. Any hyperemia related to the insertion subsides in about 60 minutes.

We place a cuff on the upper arm sans the MD probes to measure BP.

We apply a local skin heater and laser Doppler probe over each MD site.

We measure local skin temperature and skin blood flow (SkBF) throughout the MD experiments.

We also measure BP every 5-7 minutes (brachial osculation and/or Cardiocap).

Acetylcholine (ACh) Dose Response:

Two MD probes are inserted (see above)

Probe 1: Lactated Ringer's

Probe 2: Lactated Ringer's + LNAME (15mM)

Hyperemia associated with the probe insertion is allowed to subside for ~60 minutes.

Baseline SkBF data are collected for ~10 minutes.

The first concentration of ACh is added to the perfusate at sites 1 and 2.

Sites 1 and 2 receive 11 increasing concentrations of ACh (10^{-11} to 10^{-1} mM) over 75 minutes.

As SkBF stabilizes with the addition of each concentration of ACh, the next concentration of ACh is added to the perfusates.

After the last concentration of ACh, the perfusates at both sites are switched to Lactated Ringer's + SNP (28mM), and holders are heated to 43°C (109.4°F) at a rate of 0.5°C/5 seconds. Heating + SNP perfusion elicits maximum vasodilation.

SkBF stabilizes after ~20 minutes.

MD tubing is removed from the skin and sterile bandages are placed over the sites. If the participant desires, a bag of ice is placed on the MD sites for 10 minutes to reduce bruising that may occur.

Equipment

Laser Doppler Flowmetry: The Laser Doppler Flowmeter (Moor Instruments, Inc.) non-invasively provides a qualitative measure of skin blood flow to a depth of about 1 mm in the skin using a weak laser light. This measure is a dimensionless value called "flux" that reflects the speed and number of blood cells moving through the microvasculature in an area of skin. The flowmeter continuously measures skin blood flow using a fiber optic probes that fit into holders taped to the skin. *approved by the FDA*

Blood Pressure, ECG (Heart rate): The CardioCap 5 (General Electric – GE) critical care monitor measures blood pressure via a cuff inflated every 5-7 minutes on the upper arm and heart rate via 3-lead ECG probes taped to the skin of the chest. *approved by the FDA*

Flow Mediated Dilation (FMD): FMD measures the health of blood vessels. The researchers place a blood pressure cuff around the forearm. They put gel on the upper arm just above the elbow. Then they place a Doppler ultrasound probe on the gel. The ultrasound makes sound waves to measure the size of blood vessels and the speed of the blood. They make a "resting" measurement before they inflate the cuff. Then they inflate the cuff for 5 minutes to stop blood flowing to and from the forearm. After they deflate the cuff, they perform a second reading for 3 minutes. ATL HDI 5000 SonoCT (Ultrasound) *FDA 510 (k) approved by the FDA*

Fitness tests:

YMCA step test: For the YMCA step test, we will have people stepping onto a 12 inch step. They will be stepping up and down, alternating steps to a metronome set to 96 bpm, which would be stepping at a rate of 24 steps per minute. They will step up and down at that rate for 3 minutes. After the 3 minutes, the participant will immediately sit down and have their heart rate recorded for the min following the test. Participants will wear a heart rate monitor on their chest to monitor their heart rate.

YMCA cycle ergometer tests: For the cycle ergometer test, participants will wear a chest worn heart rate monitor and will cycle at a rate of 50 rpm (repetitions/minute) for two to four 3-minute stages of continuous exercise. Their heartrate response would dictate how much we increase work by and then we can use that data to extrapolate what their maximum HR response would be and their fitness (i.e., Vo2 max).

7.2.3 Intervention Period

Provide a description as defined above and format accordingly.

During the first 3-month intervention period, participants will be asked to use the Heartphone app in the field continuously. The application runs automatically, so participants will not be asked to do anything other than install and use the app for the next three months and to wear their Fitbit activity monitor.

7.2.4 Lab Visit 2 (Month 3)

Three months following the baseline visit, participants will be asked to return to the lab to repeat measures taken during the baseline assessment. The researcher will remove the HeartPhone app from the participant's phone. Participants will be set up with an Actigraph accelerometer and given a 1-week wear log to record their activity for one week. Participants will then mail the accelerometer back at the end of the week.

A modification is proposed to include additional questions in the questionnaire pertaining to the acceptability of the Heartphone app. We will also engage in a brief semi-structured interview with the participants at this time to further gauge their experience using the HeartPhone app. The additional questions to be included in the questionnaire and semi-structured interview guide have been uploaded in the Other Attachments section of the Local Site Documents.

7.2.5 Lab Visit 3 (Month 6)

Participants will then be asked to come back into the lab one final time approximately 6 months following their initial baseline visit. All measures taken at baseline and 3 months will again be taken at 6 months.

7.3 Duration of Participation

Describe the duration of an individual subject's participation in the study.

It is anticipated that participation in the study will take approximately two hours each visit for those enrolled in the main study. Participation in the ancillary study will take approximately 7 hours total (2 hours for all the main study assessments plus an additional 5 hours for the ancillary study assessments). Participants enrolled in the ancillary study will be given the option to complete the main study protocol and the ancillary study protocol on separate days if they wish.

7.4 Test Article(s) (Study Drug(s) and/or Study Device(s))

7.4.1 Description

Provide a brief description of all test articles (drugs (including any foods and dietary supplements), devices and/or biologics used in the research including the purpose of their use and their approval status with the Food and Drug Administration (FDA). Include information about the form of the drug product (e.g., tablets, capsules, liquid).

Acetylcholine

ACh

Form: Solid

Role in Current Study: Local heating combined with the local perfusion of endothelial agonist, acetylcholine, specifically examines the attenuated endothelium-dependent vasodilation (eNOS-derived NO) associated with vascular pathologies.

Concentration: 10⁻¹¹ to 10^{-1M}

LNAME N^G-nitro-L-arginine methyl ester Form: Solid
Role in current study: A nitric oxide synthase inhibitor. L-NAME is an analog to the amino acid, L-arginine. L-NAME is a non-specific inhibitor for nitric oxide synthases, thereby inhibiting the production of nitric oxide (NO) that causes vasodilation. We deliver small doses of LNAME to a nickel-sized area of the skin.
Concentration: 15mM

Sodium Nitroprusside SNP Form: Solid
Role in Current Study: SNP, acting an NO donor, dilates blood vessels maximally thereby achieving maximal SkBF. Maximal SkBF is a reference point for other measures of SkBF.
Concentration: 28mM

Lactated Ringer's Ringer's Form: Liquid
Role in current study: Lactated Ringer's acts as the vehicle for the investigative substances and as a flush.

7.4.2 Treatment Regimen

Describe dose, route of administration and treatment duration. Include information about dose adjustments.

Investigative Substances: Microdialysis

The following is a table of the research agents used with intradermal microdialysis

Drug	Concentration (mM)	Treatment Duration (min)	Dose (14% Delivery, mg)
ACH	1.00E-01	5	2.54E-02
ACH	1.00E-02	5	2.54E-03
ACH	1.00E-03	5	2.54E-04
ACH	1.00E-04	5	2.54E-05
ACH	1.00E-05	5	2.54E-06
ACH	1.00E-06	5	2.54E-07
ACH	1.00E-07	5	2.54E-08
ACH	1.00E-08	5	2.54E-09
ACH	1.00E-09	5	2.54E-10
ACH	1.00E-10	5	2.54E-11
ACH	1.00E-11	5	2.54E-12
L-NAME	1.50E-02	85	0.96E-01
SNP	2.80E-02	30	7.00E-02

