1.3 Secondary Study Endpoints

State the secondary endpoints to be measured in the study.

1. Total PA Volume: Fitbit Charge 2 HR (step counts) worn from baseline to 3 months
2. MVPA: Actigraph GT3XP-BTLE (bout frequency & duration)
3. Automatic affective evaluations of PA: Single-Category Implicit Association Test in lab
4. Reflective affective judgments of PA: Physical Activity Enjoyment Scale; Behavioral Regulations in Exercise Questionnaire-2+ via self-reports in lab
5. Cardiac reserve; fitness capacity: 3-min step test; predicted VO₂max
6. Cycle ergometer
7. Cardiovascular health: Cardiometabolic panel via phlebotomy (15 mL serum sampling)
8. Macrovascular function: Brachial artery flow-mediated vasodilation
9. Microvascular function: Cutaneous microcirculatory assessment of NO-mediated vasodilation acetylcholine dose-response with/without NO-synthase inhibition (L-NAME)

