When mixing the perfusates, the lab personnel performing microdialysis washes their hands, wears protection (e.g. gloves, lab coat), and uses glassware that has been washed with cleanser (Alconox, designed for use with healthcare instruments, pharmaceutical process equipment, tissue culture apparatus, etc.), and rinsed multiple times in tap water and then doubly-distilled water and air-dried. The solid investigational agents are weighed on a microbalance and then mixed with sterile pharmaceutical-grade lactated Ringer's solution to the desired concentration (See **Treatment Regimen**). The solution is drawn into a syringe through a 0.2 μ m filter. Prior to injecting a solution into or withdrawing a solution from a sterile container through a sterile hypodermic needle, the stopper of the sterile container is cleaned thoroughly with alcohol. The final dilutions of the perfusates are drawn into sterile syringes through 0.2 μ m filters within minutes or hours of their use in the experiment.

The lab personnel performing microdialysis will use the study treatments in the microdialysis experiments.

7.4.6.4

Return or Destruction of the Test Article

Describe the procedures for final reconciliation of the test article supply at the end of the study and whether the test article is to be shipped back to a source or destroyed on site.

Investigative substances are usually consumed in the experiments. Investigative substances not consumed by the experiments are disposed of in accordance with the policies of Environmental Health and Safety of Penn State. Some substances (e.g. protein or peptide-based) are autoclaved prior to disposal.

7.4.6.5

Prior and Concomitant Therapy

Describe what prior and/or concomitant medical therapy will be collected. Describe which concomitant medicines/therapies are permitted during the study. Describe which concomitant medicines are not permitted during the study.

Not applicable.

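### The perfusate table in 7.4.2 is labelled mM, but its L-NAME and SNP entries match the concentrations in the text only as M, a 1000-fold difference; the ACh unit needs confirming.

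*Combined protocol and SAP*

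**What the plan says.** Three places in the combined protocol and SAP give perfusate concentrations.

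- Section 7.4.2 (Treatment Regimen) tabulates drug, concentration, minutes and dose in mg at 14% delivery. The concentration column is headed "Concentration (mM", with the bracket then closed. It lists eleven ACh rows from 1.00E-11 to 1.00E-01, L-NAME at 1.50E-02 and SNP at 2.80E-02.
- Section 7.4.1 (Description) gives L-NAME as "Concentration: 15mM" and SNP as "Concentration: 28mM". Its ACh line has the same exponents as the table, but with M as the unit.
- Section 7.2.2 (Lab Visit 1) also has 15 mM for L-NAME and 28 mM for SNP. For ACh it says: "Sites 1 and 2 receive 11 increasing concentrations of ACh (10^{-11} to 10^{-1} mM) over 75 minutes".

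Section 7.4.6.3 (Preparation and Dispensing) tells staff to weigh the solids and mix them "to the desired concentration (See Treatment Regimen", closing the bracket. That is the title of 7.4.2, so the table is the mixing reference.

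Secondary endpoint 9 in section 1.3 is the "acetylcholine dose-response with/without NO-synthase inhibition (L-NAME" measurement of microvascular function. Section 7.4.1 says of the SNP step: "Maximal SkBF is a reference point for other measures of SkBF".

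**The concern.** The same two drugs carry the same digits in three places, but the table's unit label makes its values a thousandth of the others. The table is also where the preparation instructions point. A preparer who follows the label would make L-NAME at 0.015 mM and SNP at 0.028 mM.

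The L-NAME site is what separates NO-mediated dilation from the rest of the ACh response. If the inhibitor is 1000-fold too weak, the with/without contrast no longer measures what endpoint 9 names. SNP helps set the maximal flow against which other flow values are read, so a weak SNP solution could also affect that reference. With ten participants and three visits each, there is little room to lose sessions.

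For ACh the text itself gives two units, so a careful preparer could not settle the matter from the prose.

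**Working it through.** **1. L-NAME and SNP: unit conversion only.** Inputs are the 7.4.2 entries and the concentrations in 7.2.2 and 7.4.1.

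| Agent | Table entry | As labelled (mM) | If M, in mM | Text (mM) | Text / labelled |
|---|---|---|---|---|---|
| L-NAME | 1.50E-02 | 0.015 | 15 | 15 | 15 / 0.015 = 1000 |
| SNP | 2.80E-02 | 0.028 | 28 | 28 | 28 / 0.028 = 1000 |

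Both entries miss by exactly 1000 as labelled and match exactly as M. That is the pattern of a wrong header, not of two wrong values.

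**2. ACh: does the table use one unit throughout?** Dose in mg is proportional to concentration x minutes x molar mass x perfusion rate x delivery fraction. Dividing the listed mg by concentration and minutes leaves molar mass x rate x a constant:

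- ACh, top step: 0.0254 / (0.1 x 5) = 0.0508
- L-NAME: 0.096 / (0.015 x 85) = 0.0753
- SNP: 0.070 / (0.028 x 30) = 0.0833

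The ratios to ACh are 0.0753 / 0.0508 = 1.48 and 0.0833 / 0.0508 = 1.64. If ACh alone were in mM and the other two in M, the ACh figure per M would be 0.0508 x 1000 = 50.8. At a common perfusion rate, ACh would then have to be 50.8 / 0.0753 = 675 times as heavy per mole as L-NAME, and 50.8 / 0.0833 = 610 times as heavy as SNP. One shared unit is far more credible. Step 1 fixes that unit as M for L-NAME and SNP, so the mg column is consistent with M for ACh too.

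**3. Supporting check on assumed molar masses.** The documents give neither molar masses nor a perfusion rate, so this step is illustrative. Rate = mg / (concentration x minutes x molar mass x 0.14).

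- With assumed salt forms (ACh 181.66, L-NAME 269.69, SNP 297.95 g/mol), the implied rates are 1.997, 1.994 and 1.998 uL/min if the column is M, and 1997, 1994 and 1998 uL/min if it is mM.
- With assumed base, ion or anhydrous forms, the rates run from 2.27 to 2.48 uL/min if M, and from about 2273 to 2482 uL/min if mM.

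Under either set, the three agents imply similar rates. The mM reading needs a rate of 2 mL/min or more. For L-NAME, 1994 uL/min x 85 min is about 170 mL through one skin probe, which does not fit the small local amounts described in section 11.0.

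**The case against.** The intended L-NAME and SNP values are each stated twice with explicit units, in the step-by-step procedure and in the drug description just before the table. The mg column appears to have been computed from M, so the underlying numbers look right and only the label is wrong. Section 7.4.6.3 puts preparation under physician oversight with a separate SOP, and section 11.0 says the FDA accepted the researchers' technique for preparing perfusates. All of this stands. It makes mis-mixing less likely, but it does not correct the table that preparers are told to use.

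Four stronger readings are tempting and are not supported.

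- *Maximal dilation would be lost.* Section 7.2.2 attributes maximum vasodilation to SNP together with heating to 43°C, and section 11.0 describes local heating as the means of determining maximal flow. The documents do not say how far the maximum would fall with weak SNP. The supportable claim is that it could be weakened.
- *The ACh range is wrong by 1000.* Section 7.2.2 agrees with the table header. The contrary line in 7.4.1 is garbled in extraction, although M is legible without a milli prefix. The mg argument assumes a common perfusion rate that is nowhere stated. This is a unit to confirm, not an established error.
- *The eleven 5-minute ACh rows (55 min) contradict the 75 min in 7.2.2.* The procedure says "As SkBF stabilizes with the addition of each concentration of ACh, the next concentration of ACh is added to the perfusates", so step length follows the response and 5 min can be nominal. The 85 min listed for L-NAME equals the roughly 10 min baseline plus 75 min, so the table already accommodates the longer period.
- *Participants are at risk.* Following the label gives too little drug. No overdose is shown, and nothing shows that anyone has mixed to the label.

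**Conclusion.** The table header is wrong as written for L-NAME and SNP, by a factor of exactly 1000 against two other sections. This rests on unit conversion alone and is firm. That all rows share M, including ACh, is likely but conditional on a common perfusion rate, so the ACh unit stays open until the sponsor confirms it.

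If the label were followed, the NO-synthase inhibition contrast in secondary endpoint 9 would be compromised and the maximal-flow reference might be weakened. How much blockade 0.015 mM L-NAME would leave is not something the documents allow one to calculate. The reach is limited to one secondary endpoint in the ancillary study of 10; the primary endpoint, its power statement and the main analysis are untouched. It is worth correcting because the faulty label sits in the mixing reference and the correction is small.

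**What to change.** Either change the concentration header in 7.4.2 to M, or keep mM and convert the entries (L-NAME 15, SNP 28). Check the ACh unit against the IND submission described in section 17.1, and make 7.2.2, 7.4.1 and 7.4.2 agree. If M is confirmed, the 7.2.2 range changes to M; in a table kept in mM, the ACh rows would run from 1E-08 to 100.

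The cost is an amendment to one table header or column, and to the ACh unit wherever it proves wrong. Participants, visits and analysis do not change.
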